4.6 End of Study Definition

The end of the study is defined as 3 months after the completion of the final data capture (i.e. final data collection with final participant). The CI will notify the REC that the trial has ended and a summary of the trial report will be provided within 12 months of the end of trial.

5. Laboratories (if Applicable)

Not applicable

6. Assessment of Safety

The collection and reporting of adverse events (AEs) and Serious Adverse Events (SAEs) will be in accordance with Good Clinical Practice and the Research Governance Framework 2005. Definitions will be as defined in the Guys and St Thomas Foundation NHS Trust Standard Operating Procedures for the Identifying, Recording and Reporting Adverse Events.

Safety will be assessed continuously throughout the trial. There are no Investigational Medicinal Products being used as part of the MOSAIC study.

There may be a small increased risk of a temporary increase in pain on walking during the assessment and completion of MOSAIC as it is a requirement of the walking exercise that pain is

induced within 3-5 minutes of commencing walking. Physiotherapists are trained to identify and address any untoward increases in pain. No other risks are expected to arise from taking part in the trial. It is therefore, reasonable to collect only targeted treatment-related AEs.

Adverse events (AEs)) will be recorded from date of consent to the 6 month outcome assessment.

All AEs will reported to the CI.

Physiotherapists treating participants randomized to MOSAIC will be trained to identify and report AEs in a standard format.

All participants will report AEs to the RA at follow up assessments (in response to one open ended question "Have you had any problems since your last assessment /questionnaires?"). These will be reported by the RA in a standard format.

Serious Adverse Events

Investigators (or their delegates) should contact the CI within 24 hours of becoming aware of a suspected SAE.

Participants will be contacted by the PI and the PI will decide whether a SAE has occurred and act in accordance to Safety Reporting in Non-CTIMP Research Stand operating procedures (Appendix 1). The PI will be also asked to provide a categorisation of seriousness and causality. The form should be sent to the CI and a copy kept in the site file.

Investigators should also report SAEs to their own Trust in accordance with local practice.

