5.4 Adverse events

Safety will be assessed continuously throughout the trial. There are no investigational medicinal products being used as part of the MOSAIC trial.

There may be a small increased risk of a temporary increase in pain on walking during the assessment and completion of MOSAIC as it is a requirement of the walking exercise that pain is induced within 3 to 5 minutes of commencing walking. Physiotherapists are trained to identify and address any untoward increases in pain. No other risks are expected to arise from taking part in the trial. It is therefore, reasonable to collect only targeted treatment-related AEs (AEs).

The collection and reporting of AEs and Serious Adverse Events (SAEs) will be in accordance with Good Clinical Practice and the Research Governance Framework 2005. Definitions will be as defined in the Guys and St Thomas Foundation NHS Trust Standard Operating Procedures for the Identifying, Recording and Reporting Adverse Events.

AEs will be recorded from date of consent to the 6-month outcome assessment. All AEs will be reported to the CI. Physiotherapists treating participants randomised to MOSAIC will be trained to identify and report AEs in a standard format.

All participants will report AEs to the Research Associate (RA) at 3 and 6 month follow up assessments (in response to one open ended question "Have you had any problems since your last assessment /questionnaires?" These will be reported by the RA in a standard format.

The number of AEs will be reported with proportions and 95% confidence intervals for differences between the groups, where appropriate.

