7.2 Secondary Endpoints

The difference in mean walking ability at 6 months between the intervention and comparison groups, adjusted for baseline walking ability and site.

The difference in QoL at 6 months between the intervention and comparison groups, adjusted for baseline QoL and site.

The difference in activities of daily living at 6 months between the intervention and comparison groups, adjusted for baseline activities of daily living and site.

The MCIDs for the following measures will be calculated: 6MWD, SR-MWD, WELCH, NEADL, VascuQol-6.

8 Sample Size Considerations

Based on previous work, 192 participants will be required to detect a mean 6MWD difference of 58 metres (standard deviation (SD) =111; α =0.05; 1- β =0.90) accounting for 20% attrition at 3 months follow up.

9 Analysis Sets

The definitions of different analysis populations are shown below:

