10.1 General Methodology

All analyses will not be carried out unless the trial database has been authorised as complete and final, and all protocol deviations have been identified.

The analyses will be performed by the trial statistician and the primary analysis will be reviewed by a second statistician. ITT will be the main strategy of analysis adopted for the primary outcome and the secondary outcomes 1a; 1b and 3. Also, all regression analysis will include the stratification factor, centre, as a covariate.

Continuous data will be summarised in tables using descriptive statistics, including the number of participants, mean, standard deviation, median and range as appropriate. Summaries of continuous characteristics will be based on non-missing observations. For categorical variables, counts and percentage per treatment group will be presented. Percentage for categorical variables will be calculated based on number of patients with non-missing values for the variable. Range checks of the data will be performed to identify anomalous values.

All statistical hypothesis testing will be done using two-sided tests with type I error of 0.05, unless otherwise stated.

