11.1.5 Subgroup analyses

There are no planned subgroup analyses.

12 Baseline data analysis

Histograms will be produced for continuous variables and summarised using mean, standard deviation, number with median and range if the data are very skewed.

Categorical data will be summarised by frequencies and percentages.

The number of AEs and SAEs will be reported with proportions and 95% confidence intervals for differences between the groups where appropriate.

13 Software

Statistical analysis: Stata 15 or (later if there is an update before analysis), will be used for data analysis.

14 Bibliography

- 1. Montgomery, P.S.a.G., A.W., *The Clinical Utility of a Six-Minute Walk Test in Peripheral Arterial Occlusive Disease Patients.* Journal of the American Geriatrics Society, 1998. **46**(6): p. 706-711.
- 2. Society, A.T., *American Thoracic Society Statement: Guidelines for the Six-Minute Walk Test* American Journal of Respiratory and Critical Care Medicine, 2002. **166**(1).
- Jaeschke; R., S., J., Guyatt, G. H., Measurement of Health Status Ascertaining the Minical Clinically Important Difference Controlled Clinical Trials, 1989. 10(4): p. 407-415.
- 4. Juniper, E.F., et al., *Determining a minimal important change in a disease-specific quality of life questionnaire.* Journal of Clinical Epidemiology, 1994. **47**(1): p. 81-87.
- Deyo, R.A., P. Diehr, and D.L. Patrick, *Reproducibility and responsiveness of health status measures statistics and strategies for evaluation*. Controlled Clinical Trials.
 12(4): p. S142-S158.
- 6. Wyrwich, K.W., W.M. Tierney, and F.D. Wolinsky, *Further Evidence Supporting an SEM-Based Criterion for Identifying Meaningful Intra-Individual Changes in Health-Related Quality of Life.* Journal of Clinical Epidemiology, 1999. **52**(9): p. 861-873.

	Who	When	How	To Whom
SAE	Chief Investigator	-Report to Sponsor within 24 hours of learning of the event -Report to the MREC within 15 days of learning of the event	SAE Report form for Non- CTIMPs, available from NRES website.	Sponsor and MREC

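### The between-arm adverse event comparison pools a reporting route that exists only in the MOSAIC arm, which biases it towards more adverse events in MOSAIC by an unknown amount

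*SAP*

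**What the plan says.** SAP 5.4 and Protocol section 6 (Assessment of Safety) describe two routine AE routes.

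- **Both arms.** The research associate (RA) puts one open question to every participant at the 3- and 6-month assessments. Protocol 4.2 plans for the RA to be blind to allocation.
- **MOSAIC arm only.** "Physiotherapists treating participants randomised to MOSAIC will be trained to identify and report AEs in a standard format" (SAP 5.4). Protocol section 6 says the same: "Physiotherapists treating participants randomized to MOSAIC will be trained to identify and report AEs in a standard format".

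SAP 4.3 places the MOSAIC contacts at weeks 1, 2, 6 and 12. The assessments common to both arms fall at weeks 0, 12 and 24. SAP section 3 notes that physiotherapists do not deliver usual NHS care.

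For analysis, SAP 5.4 states: "The number of AEs will be reported with proportions and 95% confidence intervals for differences between the groups, where appropriate". SAP section 12 repeats this for AEs and SAEs together: "The number of AEs and SAEs will be reported with proportions and 95% confidence intervals for differences between the groups where appropriate". Neither section splits events by source, limits the comparison to the shared question, or removes duplicates. SAEs have their own route in SAP 5.4.1, through investigators and the principal investigator. The safety set (SAP 9.3) is all participants.

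**The concern.** Randomisation makes the arms comparable in true risk, but not in how hard anyone looks for events. Here the allocation itself decides whether a participant has an additional trained reporter. Between baseline and week 12 the usual-care arm has no scheduled trial contact, while MOSAIC participants have at least three with someone trained to report AEs. The event that the plan itself anticipates, a passing increase in walking pain, is one that a single recall question at 3 months could easily miss.

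Three things then mix in one interval: any real harm, extra detection, and a blinded source pooled with one that cannot be blinded, since the physiotherapists deliver the treatment. The event count has a further problem. One event reported by both routes could appear twice, and only in MOSAIC. A reader of the resulting table could not tell harm from detection.

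**Working it through.** **1. Arm size.** The documents give no AE figure, so the only stated figure to reproduce is the sample size. SAP section 8 says "192 participants will be required to detect a mean 6MWD difference of 58 metres", with "standard deviation (SD) =111; α =0.05; 1- β =0.90", "accounting for 20% attrition at 3 months follow up". SAP 10.1 makes tests two-sided.

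n per arm = 2 × [(1.960 + 1.282) × 111 / 58]² = 76.97, so 77. Total with attrition = 2 × 76.97 / 0.8 = 192.4, which agrees with the stated 192. At 1:1 allocation this is 96 per arm randomised.

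**2. Model.** Let p be the true proportion with an AE, equal in both arms. Let s be the probability that the RA question recovers it, and q the probability that a physiotherapist independently does so.

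- Usual care records p·s.
- MOSAIC records p·[1 − (1 − s)(1 − q)].
- The spurious difference is p·q·(1 − s). It is positive whenever q > 0 and s < 1, and zero when either limit is reached.

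**3. Assumed values.** p = 10%, 20%, 30%; s = 50%, 80%; q = 30%, 50%. None of these is in the documents. Example: p = 0.20, s = q = 0.5 gives 0.20 × 0.75 = 15% against 0.20 × 0.5 = 10%.

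**4. Results.** Exact binomial enumeration, 96 per arm, Wald 95% CI for the risk difference:

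| p | s | q | MOSAIC | Usual care | Difference (points) | CI wholly above 0 |
|---|---|---|---|---|---|---|
| 10% | 50% | 30% | 6.5% | 5.0% | +1.5 | 6.9% |
| 10% | 50% | 50% | 7.5% | 5.0% | +2.5 | 11.2% |
| 10% | 80% | 30% | 8.6% | 8.0% | +0.6 | 3.7% |
| 10% | 80% | 50% | 9.0% | 8.0% | +1.0 | 4.6% |
| 20% | 50% | 30% | 13.0% | 10.0% | +3.0 | 9.6% |
| 20% | 50% | 50% | 15.0% | 10.0% | +5.0 | 18.1% |
| 20% | 80% | 30% | 17.2% | 16.0% | +1.2 | 4.1% |
| 20% | 80% | 50% | 18.0% | 16.0% | +2.0 | 5.6% |
| 30% | 50% | 30% | 19.5% | 15.0% | +4.5 | 12.8% |
| 30% | 50% | 50% | 22.5% | 15.0% | +7.5 | 26.6% |
| 30% | 80% | 30% | 25.8% | 24.0% | +1.8 | 4.9% |
| 30% | 80% | 50% | 27.0% | 24.0% | +3.0 | 7.2% |

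The median of the last column is 7.0%. With q = 0 it is 2.5% to 2.7%, close to the nominal 2.5%. At 77 per arm the differences are the same and the range is 3.6% to 23.0% (median 6.3%).

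**5. Months 3 to 6.** MOSAIC has no physiotherapist contact after week 12, so later events dilute the bias. Adding an assumed 5-10% recorded risk, equal in both arms, lowers 18% to 12-14% and 27% to 19-22%.

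**The case against.** The strongest reply is that the asymmetry may matter little.

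- Every participant gets the shared question, and an event reported there as well causes no bias in the proportion affected. If the question recovers 80% of events, the interval lies above zero in only 3.7% to 7.2% of trials. This stands: the effect can be small.
- A reader might infer that AEs are asked about at each of the four MOSAIC contacts. The session content in the Protocol's schedule of treatment lists no AE question. Detection rests on training and opportunity, and the week-12 call coincides with the 3-month assessment. This also stands.
- Case report forms, which include AEs, are completed for every participant by the principal investigator or delegates (Protocol section 9). That is a possible site route in both arms. No contact is scheduled to feed it in usual care before week 12, so it does not remove the imbalance.
- The SAP qualifies the comparison as applying where appropriate. It gives no criterion, and nothing tells the analyst that unequal ascertainment is a reason to withhold the interval.
- Only targeted treatment-related AEs are to be collected, so equal true risk is a simplification. It serves to isolate the detection component and is not a forecast.
- This is a safety summary with no decision rule attached. Effectiveness rests on the primary outcome. That limits the weight of the point but does not remove it.

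**Conclusion.** The point holds as a bias of known direction and unknown size. AE ascertainment is unequal by design, and the planned contrast pools the sources without separating or de-duplicating them. Within the assumed ranges (10-30% true risk, equal in both arms; 50-80% recovery by the question; 30-50% by physiotherapists; 96 per arm), the spurious difference is 0.6 to 7.5 points. The interval lies wholly above zero in 3.7% to 26.6% of trials, median about 7%.

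Two stronger readings are tempting and are not supported. One is that MOSAIC will look more harmful. The documents give no AE or detection rates, and the values of 18% and 27% are the two worst of the 12 scenarios. The other is that the SAE comparison is biased in the same way. SAP 5.4.1 gives SAEs an investigator route that is not tied to arm, and no such bias has been shown. The primary 6MWD analysis and the sample size are unaffected.

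**What to change.** In SAP 5.4 and section 12:

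1. Record the source of each AE (RA question, physiotherapist, other) and remove duplicates across routes.
2. Base the between-arm AE difference and its 95% CI on events elicited by the open question put to both arms at 3 and 6 months.
3. List AEs reported only by physiotherapists separately, for MOSAIC, without a between-arm interval. Show all-source totals by arm descriptively in the full safety set.
4. Report the number answering the question in each arm, and list deaths and withdrawals due to an event alongside. A responder-only denominator on its own could lose exactly those participants, and it would depart from the all-participant safety set in SAP 9.3.
5. Leave the SAE comparison in SAP 5.4.1 on all sources, with the source flagged.

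Reporting of every event to the chief investigator and the steering/monitoring committee does not change. If the question recovers events equally in both arms, the expected difference under equal true risk is zero.

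The cost is a SAP paragraph and one field on the AE form. The downside is that the AE contrast uses fewer recorded events and depends on response to the question. This is a cheap improvement to the safety reporting.

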Motivating Structured walking Activity in Intermittent Claudication (MOSAIC) is a phase II, multi-centre, parallel group, two-arm, randomised, controlled superiority trial with a 1:1 allocation ratio, stratified by recruitment site. Participants will be randomised to receive either usual National Health Service (NHS) care or MOSAIC in addition to usual NHS care.

MOSAIC comprises 2 x 60-minute individual face-to-face consultations (weeks 1 & 2) and 2 x 20-minute follow-up telephone calls (weeks 6 & 12) delivered at a convenient time and location of participant's choice (local NHS Trust or participant's home). All sessions are delivered by a trained Band 6/7 physiotherapist. A checklist outlining the components for each session will be provided to each physiotherapist. All participants randomised to receive MOSAIC will be provided with a pedometer and a patient manual which will include information on intermittent claudication (IC), risk factors, walking guidelines, goal setting, problem solving and action planning worksheets and a walking diary.

Usual care comparison: Participants randomised to the comparison group will continue to receive usual NHS care for IC which typically consists of an initial assessment, drug therapy and simple advice to walk provided by a vascular specialist and delivered in the vascular outpatient clinic. The type and duration of usual NHS care treatment received by both groups will be recorded. The opportunity for between group contamination is low as usual NHS care is not delivered by physiotherapists.

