4.3 Visit windows

The MOSAIC intervention visit windows are weeks: 1, 2, 6 and 12.

Both groups are assessed at week 0 (baseline), week 12 (3 months) and week 24 (6 months) follow up.

5 Data collection

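### The between-arm adverse-event comparison is open to ascertainment bias against MOSAIC, because one source of reports exists in that arm only and the SAP does not separate sources

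*SAP*

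**What the plan says.** **Source common to both arms.** SAP 5.4: "All participants will report AEs to the Research Associate (RA) at 3 and 6 month follow up assessments". Protocol section 6 says the same without naming the time points: "All participants will report AEs to the RA at follow up assessments". The prompt is one open question about problems since the last assessment. Under Protocol 4.4 (Follow up Procedures) it is asked at the 3-month visit and is part of the 6-month postal pack. Protocol 4.2 has the RA blind to allocation.

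**Source in MOSAIC only.** SAP 5.4: "Physiotherapists treating participants randomised to MOSAIC will be trained to identify and report AEs in a standard format". SAP 4.3 gives the contacts: "The MOSAIC intervention visit windows are weeks: 1, 2, 6 and 12". There is no counterpart in the other arm, since SAP section 3 notes that "usual NHS care is not delivered by physiotherapists".

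**Record and analysis.** Protocol section 9 describes one case report form per participant, which includes AEs and is completed by research nurse, trial physiotherapist and RA. SAP 5.4 then plans: "The number of AEs will be reported with proportions and 95% confidence intervals for differences between the groups, where appropriate". SAP section 12 repeats this for AEs and serious AEs, and SAP 9.3 defines the safety set as all participants. Nothing restricts or splits the comparison by source.

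**Scope.** SAP 5.4 calls it "reasonable to collect only targeted treatment-related AEs", yet it also says "All AEs will be reported to the CI" and puts an open question to everyone. Protocol section 6 contains the same two statements.

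**The concern.** A between-arm difference in AEs estimates a difference in risk only if events have the same chance of being recorded in each arm. Here an extra, unblinded source can add events to one arm and never to the other.

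The asymmetry touches the one harm the plan expects, a temporary increase in walking pain. A short episode in week 2 can be noted by a physiotherapist within days or weeks. In usual care it must be remembered and volunteered at the 3-month visit. If the AE table then shows more events in MOSAIC, a reader cannot tell how much of the excess is detection.

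The scope conflict adds to this. If only treatment-related events count, the plan does not say what that means in usual care or who judges it for a non-serious event. SAP 5.4.1 describes a causality assessment for serious events only.

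**Working it through.** **1. The plan's own figure.** The documents give no AE rate and no AE precision target. The only design figure is N = 192 (SAP section 8: 58 m, SD 111, two-sided α 0.05, power 0.90, 20% attrition). Normal approximation: 2 × (111 × (1.960 + 1.282) / 58)² ≈ 77 per arm, 154 in total; 154 / 0.80 = 192.5, which agrees with 192. At 1:1 this gives 96 per arm, used below.

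**2. Scheduled post-randomisation occasions on which an AE could be recorded.**
- MOSAIC: 4 physiotherapist contacts + 2 follow-up questions = 6.
- Usual care: 2 follow-up questions = 2.

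These are opportunities, not documented enquiries. The week-12 call falls in the same nominal week as the 3-month assessment, and no physiotherapist contact is scheduled after week 12.

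**3. Spurious difference when true risk is equal.** Assumed quantities, none of them in the documents:
- p = true proportion of participants with an AE, the same in both arms (0.10 to 0.40);
- s = share of those participants whom the common question identifies, the same in both arms (0.5 to 0.9);
- c = share of those missed by the question whom physiotherapists identify (0.25 to 0.75).

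Recorded proportion in usual care: p·s. In MOSAIC: p·[s + (1 − s)·c]. Spurious difference: p·(1 − s)·c, which cannot be negative.

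The 95% half-width is 1.96 × √[p₁(1 − p₁)/96 + p₀(1 − p₀)/96], where p₁ and p₀ are the recorded proportions in MOSAIC and usual care.

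| p | s | c | Usual care | MOSAIC | Spurious difference (points) | Half-width (points) | CI excludes zero |
|---|---|---|---|---|---|---|---|
| 0.10 | 0.9 | 0.25 | 9.0% | 9.25% | 0.25 | 8.1 | 5.0% |
| 0.40 | 0.9 | 0.75 | 36.0% | 39.0% | 3.0 | 13.7 | 7.1% |
| 0.30 | 0.7 | 0.50 | 21.0% | 25.5% | 4.5 | 11.9 | 11.5% |
| 0.40 | 0.5 | 0.75 | 20.0% | 35.0% | 15.0 | 12.5 | 65.6% |

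The first and last rows are the ends of the range. With good recall (s = 0.9) the excess is at most 3 points.

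**4. After the fix.** Using the common question alone sets c = 0, so the spurious difference is p·(1 − s)·0 = 0 and the interval excludes zero 5% of the time, provided s is equal in the two arms.

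**The case against.** The strongest reply is that the plan never says the sources are pooled, and that the common question may already cover the ground. At 3 months it asks about problems since the last assessment, so its recall period spans the physiotherapist contacts. A participant who reports an event there adds nothing to a participant-level proportion when a physiotherapist has also recorded it. This stands as a limit on size: the bias exists only as far as the question misses events, and it may be near zero. It does not remove the point. Pooling is an inference, but a single AE summary with no rule by source, drawn from a shared form, allows it, and the qualifier about appropriateness sets no such rule.

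A reader might infer several stronger things that the documents do not support:
- *That physiotherapists ask about AEs at all four contacts.* They are trained to identify and report AEs, but the session content in Protocol 4.4 (Schedule of Treatment) lists no AE enquiry.
- *That events before randomisation count against MOSAIC.* Recording opens at consent and randomisation follows baseline assessment, so such events balance in expectation. If included they add noise.
- *That the planned interval is invalid because it is applied to event counts.* The SAP wording can equally mean participants with an AE. The unit is ambiguous and needs stating.
- *That usual-care participants could have no countable event.* The expected pain risk is attached partly to the assessments, which both arms undergo, and the same section sends all AEs to the chief investigator. The defect is a contradiction in scope, not a restriction that clearly governs.
- *That a real excess would go unnoticed.* The combined steering and monitoring committee reviews all AEs, and serious events have a reporting route not limited to physiotherapists. What is lost is the ability to separate risk from detection in the comparison.

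**Conclusion.** The point holds as a vulnerability in the safety comparison. As written, the plan allows a spurious AE excess in MOSAIC, and under the simple model above the error runs in that direction only. Its size is unknown: zero if the common question is complete, about 0.3 to 15 points over the assumed ranges, and 4.5 points in a middle case. It would be wrong to say that the comparison is certainly biased or to attach one figure to it.

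The result assumes equal true risk, equal sensitivity of the common question in both arms, and 96 participants per arm with AE data. Participants know their allocation, so equal sensitivity is not guaranteed even after the fix.

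The conflict over AE scope is a separate matter and needs resolving whatever the size of the detection effect. The primary analysis and N = 192 are not affected.

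**What to change.** 1. Add a source field to the AE record: common question, physiotherapist, or other.
2. In SAP 5.4 and section 12, define the main between-arm comparison as the proportion of participants with at least one post-randomisation AE reported at the common 3- and 6-month question, with its 95% CI. State the denominator.
3. List physiotherapist-reported and pre-randomisation AEs separately by arm, without a between-arm interval.
4. Report serious AEs in full from all sources.
5. Reconcile, in both Protocol section 6 and SAP 5.4, the statement limiting collection to treatment-related AEs with the statement that all AEs are reported and with the open question put to everyone. If relatedness is kept, say who judges it for non-serious events and what it means in usual care.

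**Cost.** One form field, SAP wording and a protocol amendment for item 5. Fewer events enter the comparison, and physiotherapist-reported events in participants who do not answer follow-up appear only in the listing. Precision falls modestly. If the planned 20% attrition also applied to the question, 96 × 0.80 ≈ 77 per arm would contribute. At a recorded 21% in each arm the half-width would be 1.96 × √(2 × 0.21 × 0.79 / 77) ≈ 12.9 points, against 11.5 with 96 per arm. A rate model for event counts is optional.
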